3.0 Patient Eligibility

3.1 Inclusion Criteria

- 3.11 Diagnosis and previously untreated active multiple myeloma by IMWG diagnostic criteria for multiple myeloma
- 3.12 Age ≥ 18 years.
- 3.13 The following laboratory values obtained ≤ 14 days prior to registration.
- Calculated creatinine clearance (using Cockcroft-Gault equation below)* ≥ 30 mL/min
 - Absolute neutrophil count (ANC) $\geq 1000/\text{mm}^3$
 - Platelet count $\geq 75000/\text{mm}^3$
 - Hemoglobin ≥ 8.0 g/dL
 - Total bilirubin $\leq 1.5 \times \text{ULN}$
 - ALT and AST $\leq 3 \times \text{ULN}$

*Cockcroft-Gault Equation:

$$\text{Creatinine clearance for males} = \frac{(140 - \text{age})(\text{actual body weight in kg})}{(72)(\text{serum creatinine in mg/dL})}$$

$$\text{Creatinine clearance for females} = \frac{(140 - \text{age})(\text{actual body weight in kg})(0.85)}{(72)(\text{serum creatinine in mg/dL})}$$

- 3.14 Prior therapy for the treatment of solitary plasmacytoma is permitted, but >7 days should have elapsed from the last day of radiation.
NOTE: Prior therapy with clarithromycin, DHEA, anakinra, pamidronate or zoledronic acid is permitted. Any additional agents not listed must be approved by the Principal Investigator.
- 3.15 Measurable disease of multiple myeloma as defined by at least ONE of the following:
- Serum monoclonal protein ≥ 1.0 g/dL (see [Section 11.1](#) for definition)
 - >200 mg of monoclonal protein in the urine on 24 hour electrophoresis
 - Serum immunoglobulin free light chain ≥ 10 mg/dL AND abnormal serum immunoglobulin kappa to lambda free light chain ratio.
- 3.16 ECOG performance status (PS) 0 or 1 (See [Appendix I](#))
- 3.17 Provide written informed consent.
- 3.18 Negative pregnancy test done ≤ 7 days prior to registration, for women of childbearing potential only.
- 3.19a Willing to follow strict birth control measures as suggested by the study.
- 3.19a1 Female patients: If they are of childbearing potential, must agree to one of the following:
- Practice 2 effective methods of contraception, at the same time, from the time of signing the informed consent form through 90 days after the last dose of study drug, AND must also adhere to the guidelines of any treatment-specific pregnancy prevention program, if applicable, OR

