- 2) Affected immunoglobulin refers to the baseline M-protein type, that is, IgG, IgA, or IgD. Not applicable if patient “non-secretory” or if patient has no heavy chain, i.e. light chain myeloma.
- 3) Immunofixation (IF) needed only in the absence of M-spike to document CR or sCR.
- 4) FLC is required only if used to assess disease response during active phase
- 5) At the end of 4 cycles and to document CR at any time point.
- 6) End of each cycle for first 4 cycles, and then at time of disease progression.
- 7) For women of childbearing potential only. Must be done ≤ 7 days prior to registration
- 8) The diary must begin the day the patient starts taking the medication and must be completed per protocol and returned to the treating institution.
- 9) Urine Electrophoresis required after baseline only if used to assess disease response
- 10) Does not need to be repeated at Cycle 1 Day 1. Baseline values can be used for Cycle 1.
- 11) If pembrolizumab is discontinued, the patient may continue treatment with the remaining drugs and these visits do not apply.
- R) Research funded (see Section 19.0). Will be charged to study and not to patient’s account.

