██████████ If the necessary documentation is not submitted in advance of attempting patient registration, the registration will not be accepted and the patient may not be enrolled in the protocol until the situation is resolved.

When the study has been permanently closed to patient enrollment, submission of annual IRB approvals to the Registration Office is no longer necessary.

- 6.15 At the time of registration, the following will be recorded:
- Patient has/has not given permission to store and use his/her sample(s) for future research of Multiple Myeloma at Mayo.
 - Patient has/has not given permission to store and use his/her sample(s) for future research to learn, prevent, or treat other health problems.
 - Patient has/has not given permission for MCCC to give his/her sample(s) to researchers at other institutions.
- 6.16 Treatment on this protocol must commence at Mayo Clinic under the supervision of a medical oncologist/hematologist.
- 6.17 Treatment cannot begin prior to registration and must begin ≤ 14 days after registration.
- 6.18 Pretreatment tests/procedures (see Section 4.0) must be completed within the guidelines specified on the test schedule.
- 6.19 All required baseline symptoms (see Section 10.8) must be documented and graded.

6.2 Trial rules:

The clinical trial will be conducted in compliance with regulations (21 CFR 312, 50, and 56), guidelines for Good Clinical Practice (ICH Guidance E6), and in accordance with general ethical principles outlined in the Declaration of Helsinki; informed consent will be obtained from all participating patients; the protocol and any amendments will be subject to approval by the designated IRB prior to implementation, in accordance with 21 CFR 56.103(a); and subject records will be stored in a secure location and subject confidentiality will be maintained. The investigator will be thoroughly familiar with the appropriate use of the study drug as described in the protocol and Investigator's Brochure. Essential clinical documents will be maintained to demonstrate the validity of the study and the integrity of the data collected. Master files should be established at the beginning of the study, maintained for the duration of the study and retained according to the appropriate regulations.

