7.0 Protocol Treatment

7.1 Treatment Schedule

Cycle length: 28 days.

Agent	Route	Dose	Day	Retreatment
Lenalidomide	PO	25 mg*	1-21	Every 28 days
Pembrolizumab	IV	200mg	Every 21 days	Every 21 days
Dexamethasone	PO	40 mg	1, 8, 15, 22	Every 28 days

* If the patient has renal insufficiency, lenalidomide dose modifications should be made according to the following criteria:

CrCl >50 mL/min: No adjustment

CrCl 30-50 mL/min: 10 mg/day

CrCl <30 mL/min (no dialysis): 15 mg every 48 hours

CrCl <30 mL/min (dialysis): 5 mg daily (after HD (hemodialysis) on HD days)

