single 25-mg dose warfarin had no effect on the pharmacokinetics of lenalidomide. However, it is not known whether there is an interaction during clinical use.

Concomitant administration with lenalidomide 10 mg/day increased the plasma exposure of digoxin (0.5 mg, single dose) by 14%. It is not known whether the effect will be different in the therapeutic situation (higher lenalidomide doses and concomitant treatment with dexamethasone).

15.27 **Known potential toxicities:**

Pregnancy Warning: Lenalidomide is structurally related to thalidomide, a known human teratogen. Therefore, in an effort to prevent to the greatest extent possible any chance of fetal exposure, lenalidomide is available through a controlled distribution program, specifically a pregnancy prevention program called Revlimid REMS. It is contraindicated in women who are or may become pregnant. Female subjects of childbearing potential are required to submit to regular pregnancy testing, and to agree to use effective forms of birth control as outlined in study protocols. Male subjects, even those who have had a vasectomy, must agree to use a condom during sexual contact with a pregnant woman or a woman who can become pregnant.

Very Common AEs (≥10%): anemia, febrile neutropenia, leukopenia, neutropenia, thrombocytopenia, cataracts, blurred vision, abdominal pain, constipation, diarrhea, dyspepsia, nausea, vomiting, asthenia, chills, edema including peripheral, fatigue, pyrexia, abnormal liver function tests, bacterial, viral and fungal infections (including opportunistic infections), bronchitis, nasopharyngitis, sinusitis, pneumonia, rhinitis, upper respiratory tract infection, urinary tract infection weight decreased, decreased appetite, hyperglycemia, hypocalcemia, hypokalemia, arthralgia, back pain, bone pain, muscle spasms, musculoskeletal pain, myalgia, pain in extremity, dizziness, dysgeusia, headache, hypoesthesia, neuropathy peripheral, neuropathy, tremor, depression, insomnia, renal failure, cough, dyspnea, epistaxis, pharyngitis, pulmonary embolism, dry skin, pruritus, rash, and deep vein thrombosis.

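### The blood count and chemistry behind the first dose may be up to 28 days old, because the Cycle 1 Day 1 repeat is waived with no age limit

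*Combined protocol and SAP*

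**What the plan says.** Three rules in the combined protocol and SAP bear on this.

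- **Section 3.13** lists creatinine clearance, neutrophils, platelets, hemoglobin, bilirubin and transaminases under "The following laboratory values obtained ≤ 14 days prior to registration".
- **Section 6.17** states: "Treatment cannot begin prior to registration and must begin ≤ 14 days after registration".
- **Section 4.1, footnote 10**, attached to the Cycle 1 Day 1 pre-treatment column, states: "Does not need to be repeated at Cycle 1 Day 1. Baseline values can be used for Cycle 1".

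That column lists a CBC and a chemistry group that includes serum creatinine. Section 7.1 makes the lenalidomide dose depend on creatinine clearance, with cut-points at 50 and 30 mL/min; one band reads "CrCl 30-50 mL/min: 10 mg/day". Section 7.1 does not say which creatinine value is to be used for the first dose.

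**The concern.** Both time limits are counted from registration, one backwards and one forwards, and neither is counted to the first dose. The Cycle 1 Day 1 draw is what would normally bridge them, and footnote 10 makes it optional however old the baseline value is.

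The patients have active, previously untreated myeloma, so stable renal function and counts over four weeks cannot be taken for granted. Section 15.25 says that 65% to 85% of lenalidomide is excreted unchanged in urine and that exposure rises as renal function falls. A creatinine clearance that crosses 50 or 30 mL/min between screening and Day 1 could go unseen when the first dose is chosen. Only first exposure is treated this way: the Day 1 columns for Cycles 2 and 3 list a pre-treatment CBC and chemistry without the waiver.

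**Working it through.** The documents state no maximum laboratory age at first dose, so there is no figure of the plan's own to reproduce. The check has two steps.

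**Step 1. Add the windows.**

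Inputs:
- a = days from laboratory draw to registration, 0 to 14 (Section 3.13).
- b = days from registration to first treatment, 0 to 14 (Section 6.17).

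Age at first dose = a + b.

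| Draw before registration (a) | b = 0 | b = 7 | b = 14 |
|---|---|---|---|
| 0 days | 0 | 7 | 14 |
| 7 days | 7 | 14 | 21 |
| 14 days | 14 | 21 | 28 |

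The permitted range is 0 to 28 days. The ±4-day visit window (±1 day for infusions) is not added, because Section 6.17 separately caps the start of treatment.

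**Step 2. Look for any rule that forces a newer value before the first dose.**

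- *Section 6.18*: "Pretreatment tests/procedures (see Section 4.0) must be completed within the guidelines specified on the test schedule". This points back to the schedule and so to footnote 10. It adds no window of its own.
- *Section 4.1, weekly column for the first two cycles*: it lists CBC and chemistry but does not say on which day the first weekly draw falls, or that it comes before dosing.
- *Section 8.11*: its Day 1 conditions are written for starting a new cycle, and its dose-reduction text refers back to the preceding cycle. Even if applied to Cycle 1, it names neutrophils, platelets and resolution of drug-related events, omits creatinine clearance and sets no age for a value.
- *Section 7.3*: the patient returns for evaluation on infusion days and on Day 1 of each cycle. No blood draw is specified.
- *Section 10.56*: laboratory results are to be evaluated before each dose. Evaluating an existing result satisfies this.

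None of the five closes the gap. Elsewhere the protocol does count to treatment: Section 3.29l dates live vaccines to the planned start of therapy, and the note to Section 3.29a refers to administration of study drugs.

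**The case against.** The best case for the plan is that 28 days is a ceiling, that the actual gap is unknown, and that first dosing is not blind. Footnote 10 permits reuse and does not forbid a repeat. The patient is seen on Day 1, results are to be evaluated, Section 8.3 repeats the renal bands during a cycle, and chemistry is drawn weekly for two cycles. All of this is true and limits the likely harm. It does not alter what the rules allow, since none of it requires a new value before the first dose.

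A reader might infer more than the documents support:

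- **That the patient becomes ineligible if values worsen.** Section 13.8 judges eligibility as of registration. A later change does not make the patient ineligible, and re-checking Section 3.13 after registration would be a new rule.
- **That tests in the 30-day screening column can be 30 + 14 = 44 days old.** The screening headers name no anchor. Section 3.13 ties only its own list to registration.
- **That the pregnancy test can be 7 + 14 = 21 days old.** The schedule alone allows it, but Section 15.28 requires testing through the lenalidomide distribution program, which largely covers the point.
- **That the myeloma response baseline is 28 days old and biases the primary endpoint.** Section 3.15 gives no window for M-protein or free light chains, so 28 days holds only if the 14-day column is also counted from registration. If M-protein rises before treatment, an older and lower baseline makes a 90% fall harder to show, and Section 11.5 also allows a VGPR without a percentage fall. No size of bias can be given.
- **That a week of lenalidomide passes before any change is seen.** This assumes that the first weekly draw is on Day 8, which is not stated.

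**Conclusion.** The point stands for the CBC and chemistry values named in Section 3.13. Followed exactly, Sections 3.13 and 6.17 and footnote 10 allow these values, including the creatinine behind the Section 7.1 bands, to be up to 28 days old at first dose. This is an explicit permission rather than a missing detail, and a gap in the timing rules rather than a contradiction.

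The figure rests on the two windows as written and on no later rule requiring a draw. How many patients would come near the maximum cannot be estimated, because the documents give no distribution of the screening-to-start interval. The significance level, power and decision rule in Section 16.2 are unaffected. It is worth correcting because the permission falls on a value that the first dose depends on, and the correction is cheap.

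**What to change.** Amend footnote 10 so that baseline CBC and chemistry may stand in for Cycle 1 Day 1 only if drawn within a window that the sponsor states and counts to the first dose. Otherwise the CBC and chemistry already listed in that column are done before dosing.

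Reconcile Sections 3.13, 6.17, 7.1 and 8.11 with footnote 10, so that the protocol says which laboratory value governs the first dose. The length of the window and the dose rule itself are for the sponsor to settle.

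State the anchor of the 14-day screening column. If it is registration, the same limit could be applied to the baseline SPEP, UPEP and free light chains.

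The cost is a footnote change, one routine blood draw in patients who start late (plus urine where it is followed, if the limit is extended to the response tests), and an occasional short delay while results are awaited. Sample size and analysis do not change.

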4.2 Event Monitoring/Survival Follow-up

	Event Monitoring Phase ¹				
	q. 3 months until PD	At PD	After PD q. 6 months	Death	New Primary
Event Monitoring	X	X	X	X	At each occurrence

1. If a patient is still alive 3 years after registration, no further follow-up is required.

5.0 Grouping Factor: None

6.0 Registration Procedures

6.1 Registration Procedures

6.11 To register a patient, access the Mayo Clinic Cancer Center (MCCC) web page and enter the remote registration/randomization application. The registration/randomization application is available 24 hours a day, 7 days a week. Back up and/or system support contact information is available on the Web site. If unable to access the Web site, call the MCCC Registration Office at [REDACTED] between the hours of 8 a.m. and 5:00 p.m. Central Time (Monday through Friday).

The instructions for the registration/randomization application are available on the MCCC web page [REDACTED] detail the process for completing and confirming patient registration. Prior to initiation of protocol treatment, this process must be completed in its entirety and a MCCC subject ID number must be available as noted in the instructions. It is the responsibility of the individual and institution registering the patient to confirm the process has been successfully completed prior to release of the study agent. Patient registration via the registration/randomization application can be confirmed in any of the following ways:

- Contact the MCCC Registration Office [REDACTED]. If the patient was fully registered, the MCCC Registration Office staff can access the information from the centralized database and confirm the registration.
- Refer to “Instructions for Remote Registration” in Section “Finding/Displaying Information about A Registered Subject.”

6.12 Correlative Research:
A mandatory correlative research component is part of this study (under IRB#521-93), the patient will be automatically registered onto this component (see Sections 3.19c and 14.0).

6.13 Prior to accepting the registration, registration/randomization application will verify the following:

- IRB approval at the registering institution
- Patient eligibility
- Existence of a signed consent form

- Existence of a signed authorization for use and disclosure of protected health information

- 6.14 Documentation of IRB approval must be on file in the Registration Office before an investigator may register any patients.

In addition to submitting initial IRB approval documents, ongoing IRB approval documentation must be on file (no less than annually) at the Registration Office

██████████ If the necessary documentation is not submitted in advance of attempting patient registration, the registration will not be accepted and the patient may not be enrolled in the protocol until the situation is resolved.

When the study has been permanently closed to patient enrollment, submission of annual IRB approvals to the Registration Office is no longer necessary.

- 6.15 At the time of registration, the following will be recorded:
- Patient has/has not given permission to store and use his/her sample(s) for future research of Multiple Myeloma at Mayo.
 - Patient has/has not given permission to store and use his/her sample(s) for future research to learn, prevent, or treat other health problems.
 - Patient has/has not given permission for MCCC to give his/her sample(s) to researchers at other institutions.
- 6.16 Treatment on this protocol must commence at Mayo Clinic under the supervision of a medical oncologist/hematologist.
- 6.17 Treatment cannot begin prior to registration and must begin ≤ 14 days after registration.
- 6.18 Pretreatment tests/procedures (see Section 4.0) must be completed within the guidelines specified on the test schedule.
- 6.19 All required baseline symptoms (see Section 10.8) must be documented and graded.

6.2 Trial rules:

The clinical trial will be conducted in compliance with regulations (21 CFR 312, 50, and 56), guidelines for Good Clinical Practice (ICH Guidance E6), and in accordance with general ethical principles outlined in the Declaration of Helsinki; informed consent will be obtained from all participating patients; the protocol and any amendments will be subject to approval by the designated IRB prior to implementation, in accordance with 21 CFR 56.103(a); and subject records will be stored in a secure location and subject confidentiality will be maintained. The investigator will be thoroughly familiar with the appropriate use of the study drug as described in the protocol and Investigator's Brochure. Essential clinical documents will be maintained to demonstrate the validity of the study and the integrity of the data collected. Master files should be established at the beginning of the study, maintained for the duration of the study and retained according to the appropriate regulations.

7.0 Protocol Treatment

7.1 Treatment Schedule

Cycle length: 28 days.

Agent	Route	Dose	Day	Retreatment
Lenalidomide	PO	25 mg*	1-21	Every 28 days
Pembrolizumab	IV	200mg	Every 21 days	Every 21 days
Dexamethasone	PO	40 mg	1, 8, 15, 22	Every 28 days

* If the patient has renal insufficiency, lenalidomide dose modifications should be made according to the following criteria:

CrCl >50 mL/min: No adjustment

CrCl 30-50 mL/min: 10 mg/day

CrCl <30 mL/min (no dialysis): 15 mg every 48 hours

CrCl <30 mL/min (dialysis): 5 mg daily (after HD (hemodialysis) on HD days)

7.2 Lack of Response

Patients will go off treatment to event monitoring if an MR is not seen after 2 cycles and a PR is not seen after 4 cycles. Confirmation of MR or PR is not required.

7.3 Patient return to Mayo Clinic

For this protocol, the patient must return to the consenting institution (Mayo Clinic) for evaluation every 21 days on the days of infusion while receiving pembrolizumab. (If pembrolizumab has been discontinued these visits are not required.) In addition, the patient must return every 28 days on Day 1 of each cycle while receiving any study treatment. Treatment by a local medical doctor (LMD) is not allowed.

7.4 Stem cell collection and transplant

Patients are allowed to collect stem cells and proceed to transplant any time after 4 cycles of initial therapy. If patient goes to transplant, they will go directly to event monitoring per Section 4.2 and the transplant should be reported on the event monitoring form. In the case that patients are unable to go to transplant due to other reasons, they can continue on study. In those cases, therapy may be interrupted for up to 4 weeks for the purpose of stem cell collection. Stem cells can be collected using standard institutional protocols. Any delay beyond 4 weeks should be discussed with the study PI prior to reinitiating protocol therapy.

8.0 Dosage Modification Based on Adverse Events

Strictly follow the modifications in this table for the first **two** cycles, until individual treatment tolerance can be ascertained. Individual drugs can be dose reduced as per the table below depending on the adverse event attribution. Thereafter, these modifications should be regarded as guidelines to produce mild-to-moderate, but not debilitating, side effects. If multiple adverse events are seen, administer dose based on greatest reduction required for any single adverse event observed. Reductions apply to treatment given in the preceding cycle and are based on adverse events observed since the prior dose.

ALERT: ADR reporting may be required for some adverse events (See Section 10)

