8.1 Dose Levels for each drug in the combination

	Pembrolizumab (Every 21 days)	Lenalidomide (Days 1-21)	Dexamethasone (Days 1, 8, 15, 22)
Starting dose	200 mg	25 mg	40 mg
-1		15 mg	20 mg
-2		10 mg	12 mg
-3		5 mg	4 mg
-4		Discontinue	Discontinue

Note: If pembrolizumab is discontinued, the patient may continue treatment with the remaining drugs. If lenalidomide is discontinued, patient will go to event monitoring.

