8.11 Instruction for initiation of a new cycle of therapy

A new cycle of treatment may begin on the scheduled Day 1 of a new cycle if:

- The ANC is $\geq 1000/\mu\text{L}$
- The platelet count is $\geq 50,000/\mu\text{L}$
- Any other non-hematologic drug-related adverse event that may have occurred has resolved to \leq Grade 1 or baseline severity.

If these conditions are not met on Day 1 of a new cycle, dosing should be delayed for 1 week. At the end of that time, the patient should be re-evaluated to determine whether the criteria have been met. If the patient continues to fail to meet the above-cited criteria, delay therapy and continue to re-evaluate.

If any drug dosing was halted during the previous cycle and was restarted with a one-level dose reduction without requiring an interruption for the remainder of the cycle, then that reduced dose level will be initiated on Day 1 of the new cycle.

If any drug dosing was omitted for the remainder of the previous cycle or if the new cycle is held due to known hematologic toxicity newly encountered on the scheduled Day 1, then the new cycle will be started with a one-level dose reduction. If a new cycle of therapy cannot be restarted within 4 weeks of the scheduled Day 1 due to non-resolution of drug related toxicities, the patient will be removed from protocol therapy and will go to event monitoring.

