8.2 Dose modifications for pembrolizumab based on adverse events during a cycle

→ → Use the NCI Common Terminology Criteria for Adverse Events (CTCAE) version 4.0* unless otherwise specified ← ←

CTCAE System/Organ/Class (SOC)	Adverse Event	Omit Pembrolizumab for Grade	Timing for Restarting Pembrolizumab	Pembrolizumab Discontinuation
Gastrointestinal disorders	Diarrhea or Colitis	2-3	AE resolves to Grade 0-1	AE does not resolve within 12 weeks of last dose or inability to reduce corticosteroid to 10 mg or less of prednisone or equivalent per day within 12 weeks
		4	Permanently discontinue pembrolizumab	Permanently discontinue pembrolizumab
Investigations	AST, or ALT, or Blood bilirubin	2	AE resolves to Grade 0-1	AE does not resolve within 12 weeks of last dose.
		3-4	Permanently discontinue pembrolizumab	Permanently discontinue pembrolizumab
Metabolism and nutrition disorders	Glucose intolerance (Type 1 diabetes mellitus [if new onset]) or Hyperglycemia	T1DM or 3-4	Omit pembrolizumab for new onset Type 1 diabetes mellitus or Grade 3-4 hyperglycemia associated with evidence of beta cell failure	Resume pembrolizumab when patients are clinically and metabolically stable.
Endocrine disorders	Endocrine disorders – Other, specify: Hypophysitis	2-4	AE resolves to Grade 0-1. Therapy with pembrolizumab can be continued while endocrine replacement therapy is instituted	AE does not resolve within 12 weeks of last dose or inability to reduce corticosteroid to 10 mg or less of prednisone or equivalent per day within 12 weeks
Endocrine disorders	Hyperthyroidism	3	AE resolves to Grade 0-1	AE does not resolve within 12 weeks of last dose or inability to reduce corticosteroid to 10 mg or less of prednisone or equivalent per day within 12 weeks
		4	Permanently discontinue pembrolizumab	Permanently discontinue pembrolizumab

CTCAE System/Organ/Class (SOC)	Adverse Event	Omit Pembrolizumab for Grade	Timing for Restarting Pembrolizumab	Pembrolizumab Discontinuation
Endocrine disorders	Hypothyroidism		Therapy with pembrolizumab can be continued while thyroid replacement therapy is instituted	Therapy with pembrolizumab can be continued while thyroid replacement therapy is instituted
General disorders and administration site conditions	Infusion related reaction	2 ^a	AE resolves to Grade 0-1	Permanently discontinue pembrolizumab if AE develops despite adequate premedication
		3-4	Permanently discontinue pembrolizumab	Permanently discontinue pembrolizumab

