Respiratory, thoracic and mediastinal disorders	Pneumonitis	2	AE resolves to Grade 0-1	AE does not resolve within 12 weeks of last dose or inability to reduce corticosteroid to 10 mg or less of prednisone or equivalent per day within 12 weeks
		3-4	Permanently discontinue pembrolizumab	Permanently discontinue pembrolizumab
Renal and urinary disorders	Acute kidney injury or Chronic kidney disease (e.g. Renal failure or Nephritis)	2	AE resolves to Grade 0-1	AE does not resolve within 12 weeks of last dose or inability to reduce corticosteroid to 10 mg or less of prednisone or equivalent per day within 12 weeks
		3-4	Permanently discontinue pembrolizumab	Permanently discontinue pembrolizumab
	All Other Drug-Related Adverse Events ^b	3 or severe	AE resolves to Grade 0-1	AE does not resolve within 12 weeks of last dose or inability to reduce corticosteroid to 10 mg or less of prednisone or equivalent per day within 12 weeks
		4	Permanently discontinue pembrolizumab	Permanently discontinue pembrolizumab

Note: Permanently discontinue for any severe or Grade 3 (Grade 2 for pneumonitis) drug-related AE that recurs, or any lifethreatening event.

a If symptoms resolve within one hour of stopping drug infusion, the infusion may be restarted at 50% of the original infusion rate (e.g., from 100 mL/hr to 50 mL/hr). Otherwise dosing will be held until symptoms resolve and the subject should be premedicated for the next scheduled dose (Section 9.9f).

b Patients with intolerable or persistent Grade 2 drug-related AE may hold study medication at physician discretion. Permanently discontinue study drug for persistent Grade 2 adverse reactions for which treatment with study drug has been held, that do not recover to Grade 0-1 within 12 weeks of the last dose.

* Located at http://ctep.cancer.gov/protocolDevelopment/electronic_applications.ctc.htm

** Use the following to describe actions in the Action column:

- Omit = The current dose(s) for the specified drug(s) during a cycle is skipped. The patient does not make up the omitted dose(s) at a later time
- Hold/Delay = The current dose(s) of all drugs during a cycle is delayed. The patient does make up the delayed dose(s) when the patient meets the protocol criteria to restart drugs
- Discontinue = The specified drug(s) are totally stopped

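### After cycle 2, Section 8.0 turns the dose modifications into guidelines without exempting the permanent pembrolizumab stops in 8.2, so the text conflicts on whether those stops bind

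*Combined protocol and SAP*

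**What the plan says.** Section 8.0 opens with "Strictly follow the modifications in this table for the first" two cycles, until individual tolerance is known. It continues: "Thereafter, these modifications should be regarded as guidelines to produce mild-to-moderate, but not debilitating, side effects". No drug, grade or type of action is excepted.

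Section 8.2 falls under that heading and is titled "Dose modifications for pembrolizumab based on adverse events during a cycle". It contains three kinds of permanent stop, none limited to particular cycles:

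- **Grade-based stops for seven event types:** Grade 4 diarrhea or colitis; Grade 3–4 AST, ALT or bilirubin; Grade 4 hyperthyroidism; Grade 3–4 infusion reaction; Grade 3–4 pneumonitis; Grade 3–4 renal events; and any other Grade 4 drug-related event.
- **A note to the table:** "Permanently discontinue for any severe or Grade 3 (Grade 2 for pneumonitis) drug-related AE that recurs, or any lifethreatening event".
- **A time limit in seven rows:** pembrolizumab ends if the "AE does not resolve within 12 weeks of last dose". The rows are diarrhea/colitis, AST/ALT/bilirubin, hypophysitis, hyperthyroidism, pneumonitis, renal, and all other drug-related events.

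The action definitions under 8.2 state "Discontinue = The specified drug(s) are totally stopped". Section 8.1 lists pembrolizumab at 200 mg with no reduced level, and adds: "If pembrolizumab is discontinued, the patient may continue treatment with the remaining drugs".

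**The concern.** A Grade 3–4 liver, lung or kidney event in cycle 1 or 2 must end pembrolizumab. If the same event first arises in cycle 3 or later, 8.2 still says stop, but 8.0 says the modifications are now guidelines. An investigator could rely on 8.0 and restart the drug once the event had resolved, and the only dose to restart at is 200 mg.

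The stated reason for relaxing the rules, that tolerance is known after two cycles, fits pembrolizumab poorly. Section 15.15 predicts steady state after about 18 weeks (18 × 7 = 126 days), with about 81% of accumulation by the fourth dose. Section 15.191 warns that side effects can be life-threatening and can appear months after the drug is stopped.

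This is a matter of patient safety and consistent conduct. It does not touch the sample size, significance level or power.

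**Working it through.** The plan states no figure on this point. The check compares the text and lays out the dosing calendar.

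**1. Can the reference in 8.0 be confined to something other than 8.2?** Section 8.0 refers to a table in the singular. The next table, in 8.1, lists dose levels and no adverse-event actions. An instruction to follow modifications strictly, by adverse event and attribution, has content only if it reaches the adverse-event tables in 8.2 to 8.4. The reference is therefore unclear, and no sentence settles it.

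**2. Does another section impose the stops?**

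| Section | What it does | Bars restarting pembrolizumab after a resolved event? |
|---|---|---|
| 9.7 to 9.9e | Treatment of lung, bowel, endocrine, liver and kidney events | No rule on restarting |
| 9.9f | Stops treatment for Grade 3–4 infusion reactions, and for Grade 2 despite premedication | Yes, infusion reactions only |
| 8.11 | Removes a patient "If a new cycle of therapy cannot be restarted within 4 weeks of the scheduled Day 1 due to non-resolution of drug related toxicities" | No, if the event has resolved |
| 13.6 | Withdrawal for an adverse event, in the investigator's opinion | No |
| 13.9a | Defines a major violation by cycle 1 treatment | No |
| 16.42 | Suspends accrual on counts of Grade 4 or higher non-hematologic events | No |

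Of the seven event types with a grade-based stop, 1 is repeated outside Section 8 and 7 − 1 = 6 are not. Section 10.56 points to Appendix 4 for managing immune-related events. That appendix is not in the supplied text, so whether it repeats the other stops is unknown.

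**3. Which infusions fall after the strict period?** Inputs: 28-day cycles and 21-day pembrolizumab intervals (7.1); two strict cycles (8.0); a four-cycle primary period (16.11).

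- Strict period: 2 × 28 = 56 days. Primary period: 4 × 28 = 112 days.
- Infusion days: 1 + 21k = 1, 22, 43, 64, 85, 106, then 127.
- Days 1, 22 and 43 are within the strict period. Days 64, 85 and 106 are after it, which is 3 of 6, as is every later infusion. Day 64 is the fourth dose.

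**4. When can the 12-week limit fall due?**

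- Earliest last dose is day 1, so the limit falls due on day 1 + 84 = 85, which is 85 − 56 = 29 days after the strict period ends. On the planned schedule and a literal reading, it could never bind.
- With the maximum 4-week delays under 8.11, Cycle 2 Day 1 is 29 + 28 = day 57 and Cycle 3 Day 1 is 57 + 28 + 28 = day 113. The strict period then runs to day 112 and includes day 85.

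**5. Worked case (assumed event).** Take Grade 3 ALT on day 66, in cycle 3. Section 8.2 ends pembrolizumab. Section 9.9d gives intravenous steroid for 24 to 48 hours, then a taper of at least 4 weeks once the event is Grade 1 or less. Let t be the day on which that is reached (assumed; earliest 66 + 2 = 68). The taper ends no earlier than t + 28.

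| t | Earliest end of taper | First planned infusion on or after it |
|---|---|---|
| 68 to 78 | 96 to 106 | Day 106, within the 112-day period |
| 79 to 85 | 107 to 113 | Day 127, in cycle 5 (days 113–140) |

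Cycle 4 Day 1 is 3 × 28 + 1 = day 85. In both ranges the event has resolved by then, so 8.11 would not delay that cycle on its account.

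**The case against.** The strongest reply is that 8.0 concerns dose titration. The sentence just before the guideline wording is about reducing individual drugs, and the sentences after it speak of reductions. Pembrolizumab has no reduced level, so that language cannot operate on it. The guideline sentence also limits itself to side effects that are not debilitating, and re-exposure after Grade 3–4 pneumonitis or nephritis hardly fits that aim. Section 8.2 is specific, and its stop rows direct permanent discontinuation even in the column on restarting. Where the protocol wants discretion it says so, as in footnote b to 8.2 and the closing note of 8.4; neither extends discretion to the permanent stops. Appendix 4 may repeat the stops, and no event rate shows that anyone would be affected.

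Much of this stands as evidence of intent. The 12-week rule points the same way, since it would be nearly empty if it lapsed at day 56. That calculation starts from a cycle 1 dose, so it bears on intent and is not an example of an event first arising in cycle 3.

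It does not remove the conflict. No sentence adopts the narrower reading, and 8.1 holds no adverse-event actions to which the strict rule could apply. The reference to debilitating effects does not decide a case such as a laboratory-graded ALT rise that has resolved. Even if Appendix 4 repeated the stops, 8.0 would still need correcting.

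**Conclusion.** The concern holds. For events first arising in cycle 3 or later, 8.0 and 8.2 conflict on whether the permanent pembrolizumab stops are mandatory. A stop triggered in cycles 1–2 is not in doubt, because 8.2 defines discontinuation as total.

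The reach is half of the planned infusions in the primary period and all later ones. The possible consequence is full-dose re-exposure after a Grade 3–4 event. The practical scale is small: treatment takes place only at Mayo Clinic (7.3), with at most 41 patients (16.12). The number affected cannot be estimated, because the documents give no rate of such events for this combination.

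The conclusion rests on a literal reading of 8.0, on the planned calendar without delays, and on the supplied text without Appendix 4. Confidence is medium, because the drafters' intent was probably that the stops bind throughout. The change should be made because the ambiguity weakens a safety rule and is cheap to remove.

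**What to change.** Add to Section 8.0:

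> The guideline provision does not apply to the permanent-discontinuation rules for pembrolizumab in 8.2 (including the recurrence, life-threatening-event and 12-week rules), which are mandatory in all cycles.

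The cost is one sentence and slightly less investigator discretion over pembrolizumab in later cycles. The rules for omitting pembrolizumab doses, and all lenalidomide and dexamethasone rules, stay as they are. A patient who stops pembrolizumab may still continue the other two drugs under 8.1.
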